### **Liver Functions Plots**

A matrix scatter plot of liver function test will be plotted showing the maximum ALT, AST, ALP and total bilirubin during study period crossed against each other. Different dots will be used for randomization arm.

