### List of Key Terms

Terms	Definition of terms
Baseline	The last non-missing measurement prior to initial dosing of study drug(Screening or Day1)
Study period	Period of time from the time point when written informed consent is obtained from the subject and the end of the final assessment/observation specified in the protocol.
Treatment period	Period of time from the first study drug administration for the treatment period to the end of Week 52 visit or the end of the withdrawal visit in case of withdrawal.
Follow-up period	The follow-up period will be 4 weeks (on a per-protocol basis) starting after the early-termination visit for withdrawn subjects and after the Week 52 visit for subjects who completed the study but are not willing to enroll into the extension study. For subjects who completed the study and wish to enroll into the extension study, the follow-up period will last for a maximum of 4 weeks starting after the Week 52 visit and ending at the initiation of the extension study treatment.
Subject	An individual who participates in a clinical trial as a recipient of the study drug.
Week 12/ET	Week 12 or early termination before Week 12
Week 28/ET	Week 28 or early termination before Week 28
EOT	Week 52 or early termination before Week 52

Discontinuation	When a subject who was enrolled in the study discontinues his/her participation in the study before the completion of all the protocol-specified items of the study.
Variable	Any quantity that varies; any attribute, phenomenon or event that can have different qualitative or quantitative values.

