## 7.5 Analysis of Safety

In general, For AE Analysis up to Week 12 will be performed by Initial Randomization Set in SAF. AE Analysis from "Week 12 to the Last Evaluation" will be performed by Treatment Sequence Set in SAF. AE 100 Patient-Years analysis will be performed by Groups for Patient-Years. Details for analysis groups will be described in 10.3 Appendix3.

For other safety analysis except for AE up to Week 12 will be performed by Initial Randomization Set in SAF. For other safety analysis except for AE up to Week 52 will be performed by Treatment Sequence Set in SAF. Details for analysis groups will be described in 10.3 and 10.4.

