### 7.5.2.1 Liver Abnormalities

The following potentially clinically significant criteria in liver function tests for Alkaline Phosphatase (ALP), Alanine Transaminase (ALT), total bilirubin, Aspartate Transaminase (AST) and their combination are defined. The subject's highest value during the investigational period will be used.

Parameter	Criteria
ALT	> 3xULN
	> 5xULN
	> 10xULN
	> 20xULN
AST	> 3xULN
	> 5xULN
	> 10xULN
	> 20xULN
ALT or AST	> 3xULN
	> 8xULN
Total Bilirubin	> 2xULN
ALP	> 1.5xULN

ALT and/or AST OR Total Bilirubin (\*) (ALT and/or AST > 3xULN) or  
total bilirubin > 2xULN

ALT and/or AST AND Total Bilirubin (\*) (ALT and/or AST > 3xULN) and total bilirubin  
> 2xULN

(\*) Combination of values measured within same sample

The number and percentage of subjects with potentially clinically significant values in liver function tests during the investigational period will be presented by treatment group.

Additionally, confirmed liver abnormalities will be characterized as moderate and marked, as follow:

Moderate: ALT or AST > 3×ULN OR Total Bilirubin > 2×ULN.

Marked: ALT or AST > 3×ULN AND Total Bilirubin > 2×ULN.

Number and percentage of subjects in each category at each scheduled visit will be summarized. These combinations of elevated values are based on measured value within the same sample.

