**Table10. Visit Window for Vital signs, laboratory test (hematology, biochemistry, urinalysis)**

Time points defined in analysis	Reference date*	Acceptable time range
Screening	Day -28 to Day -1	Day -28 to Day -1
Baseline	Day 1	Day 1
Week 4 to Week 48**	Day $7 \times x + 1$	Day $(7 \times x - 6)$ to Day $(7 \times x + 8)$ and before drug administration on the visit day
Week 52	Day 365	Day 358 to Day 372
Minimum on Treatment up to Week 12***		Minimum value at allowance Range (Day 2 to Day 92) before first dose of Week 12 study drug
Maximum on Treatment up to Week 12***		Maximum value at allowance Range (Day 2 to Day 92) before first dose of Week 12 study drug
Minimum on Treatment***		Minimum value during Entire Period (No limitation for period)
Maximum on Treatment***		Maximum value during Entire Period (No limitation for period)
Week 12/ET (Week 12 or at early termination before Week 12)	Day 85	Day 2 to Day 92
Week 28/ET (Week 28 or at early termination before Week 28)	Day 197	Day 2 to Day 204
EOT (Week 52 or at early termination)	Day 365	Day 2 to Day 372

\*: Day 1 represents the first day of study treatment. The day before is expressed as Day -1.

\*\* : Represents the reference date and acceptable time range for Week x.

\*\*\*: Applied to laboratory test only.

(2) Laboratory test (fasting lipid profile test)

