Shift-from-Baseline Table for Laboratory Test Results, Fasting Lipid Profile Baseline to Lowest Value up to Week 12	X1	X3
Shift-from-Baseline Table for Laboratory Test Results, Fasting Lipid Profile Baseline to Week 12/ET	X1	X3
Shift-from-Baseline Table in Pre-Specified Reference Range Laboratory test Results by Visit, Selected Laboratory Variables		
Aspartate Aminotransferase (AST)	X1	X2
Alanine Aminotransferase (ALT)	X1	X2
Alkaline Phosphatase (ALP)	X1	X2
Total Bilirubin Category 1	X1	X2
Total Bilirubin Category 2	X1	X2
Low-Density Lipoprotein (LDL)	X1	X2
Hemoglobin (HGB) Category 1	X1	X2

Hemoglobin (HGB) Category 2	X1	X2
Hemoglobin (HGB) Category 3	X1	X2
Creatine Phosphokinase (CPK) Category 1	X1	X2
Creatine Phosphokinase (CPK) Category 2	X1	X2
Creatine Phosphokinase (CPK) Category 3	X1	X2
Creatinine	X1	X2
Absolute Neutrophil Count (ANC)	X1	X2
Lymphocytes Category 1	X1	X2
Lymphocytes Category 2	X1	X2
Platelets Category 1	X1	X2
Platelets Category 2	X1	X2
Shift-from-Baseline Table for Selected Laboratory Variables using NCI-CTCAE Toxicity Grade (version 4.0) Baseline to Week 12/ET	X1	X3
Liver Function Analysis Clinically Significant Values in Liver Function Tests	X1	X2
Summary of Moderate and Marked Liver Abnormalities by Visit	X1	X2
Liver Functions Plots	X1	X2
Vital Signs		
Vital Signs Actual and Change from Baseline	X1	X2
ECG Results by Local Investigator		
Interpretation of 12- Lead ECG Results, Assessment by Investigator Shift-from-Screening Table for 12-Lead ECG	X1	X2
Central ECG Results		
Summary of Central ECG Results Actual and Change From Baseline	X1	
Summary of Central ECG Results Change From Predose to Postdose at Week 4/ Week 8	X1	
Number and Percentage of Subjects with Categorized Central ECG Parameter Low Extreme Values	X1	
Number and Percentage of Subjects with Categorized Central ECG Parameter High Extreme Values	X1	
Number and Percentage of Subjects with Categorized Central ECG Parameter Low Extreme Values Change From Baseline	X1	
Number and Percentage of Subjects with Categorized Central ECG Parameter High Extreme Change Values Change From Baseline	X1	
Number and Percentage of Subjects with Categorized	X1	

Central ECG Parameter Low Extreme Change Values Change From Predose to Postdose at Week 4/ Week 8 Number and Percentage of Subjects with Categorized Central ECG Parameter High Extreme Change Values Change From Predose to Postdose at Week 4/ Week 8	X1	
---	----	--

X1: Placebo, 100mg, 150mg

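### SAP 7.5.2.1 sets no pre-switch cut-off for the liver-test maxima shown by randomised arm, so on-ASP015K peaks in switched placebo subjects can appear as placebo

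*SAP*

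**What the plan says.** Two liver outputs in SAP 7.5.2.1 rest on a per-subject maximum.

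- **Liver Functions Plots.** A scatter matrix "showing the maximum ALT, AST, ALP and total bilirubin during study period crossed against each other. Different dots will be used for randomization arm". In the SAP List of Key Terms the study period runs from consent to the last planned assessment, so it includes all time after a switch.
- **Potentially clinically significant values.** "The subject's highest value during the investigational period will be used". The counts for "liver function tests during the investigational period will be presented by treatment group". The SAP does not define the investigational period. The protocol's key terms extend it to completion of the last post-treatment assessment.

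SAP 7.5 gives the general rule. Through Week 12, non-AE safety uses the Initial Randomization Set. For the longer period the rule reads: "For other safety analysis except for AE up to Week 52 will be performed by Treatment Sequence Set in SAF".

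Table 18 in SAP Appendix 4 lists the row "Liver Function Analysis Clinically Significant Values in Liver Function Tests" and the liver plots twice each. Code X1 (Placebo, 100 mg, 150 mg) sits under the column that ends with Weeks 12, 12/ET and 28/ET. Code X2 (100 mg, 150 mg and four separate placebo-to-ASP015K sequences) sits under the column through Week 52 and end of treatment.

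SAP Table 10 defines a laboratory maximum up to Week 12 as "Maximum value at allowance Range (Day 2 to Day 92) before first dose of Week 12 study drug". It also defines an entire-period maximum with no limit.

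**The concern.** Placebo subjects with an inadequate response move to ASP015K at Week 12, and all who remain on placebo move at Week 28. A maximum with no end date, labelled by randomised arm, credits to placebo whatever happens on active drug afterwards. The placebo dots and the placebo column are the reference against which ALT or AST above 3 times ULN, alone or with bilirubin above 2 times ULN, will be judged. On-drug values in that reference pull the comparison toward no difference. In this plot, a combined elevation that arose on ASP015K in a switcher would be read as a placebo case.

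**Working it through.** The plan states no figure on this point, so the check compares the texts and then counts exposure.

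**1. Plot against the rest of the SAP.** The plot text says whole study period and randomisation arm. SAP 7.5 sends non-AE safety through Week 52 to the Treatment Sequence Set, SAP 7.1 presents safety by actual treatment group, and Table 18 gives the through-Week-52 plot as X2, which has no plain placebo group. The plot sentence conflicts with all three.

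**2. Highest-value table.** Table 18 asks for an X1 version. SAP 7.5.2.1 gives only the highest value in the investigational period. The shift, toxicity-grade and reference-range tables in SAP 7.5.2 each specify up to Week 12 or entire period; the liver section does not. A programmer could put the whole-period maximum in the X1 placebo column.

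**3. Week 28/ET.** The X1 column includes 28/ET. SAP 7.11.5 uses the last pre-switch value for Week 12 switchers at Weeks 4, 8, 12 and 12/ET. For Week 28 switchers the list also has 28/ET. For Week 12 switchers the general rule therefore applies at 28/ET: the value closest to Day 197 within Days 2 to 204. For a subject still in the study, that is normally a value after 28 − 12 = 16 weeks on ASP015K, shown under Placebo.

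**4. Exposure after the switch.** Protocol 5.1.1 places the visit-day dose after the assessments, so the Week 12 and Week 28 panels precede the switch. Scheduled post-baseline panels at Weeks 4, 8, …, 52 number 13.

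- Week 12 switcher: 10/13 panels = 77%; in time, 40/52 weeks = 77%.
- Week 28 switcher: 6/13 panels = 46%; in time, 24/52 weeks = 46%.
- Arm average for a fraction f switching at Week 12: [40f + 24(1 − f)]/52. With f assumed at 0.3 to 0.7, this is 55% to 68%.

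**5. Illustration on assumed rates.** The documents give neither f nor event rates. Assume a chance per panel of ALT above 3 times ULN of 0.1% on placebo and 0.4% on ASP015K, independent between panels, no dropout, and f from 0.3 to 0.7.

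| Reading of the X1 maximum | Active | Placebo arm | Ratio |
|---|---|---|---|
| Literal whole study | 1 − 0.996^13 = 5.1% | mix of 1 − 0.999^3 × 0.996^10 = 4.2% and 1 − 0.999^7 × 0.996^6 = 3.1%, giving 3.4% to 3.9% | 1.3 to 1.5 |
| All panels to Week 28 | 1 − 0.996^7 = 2.8% | mix of 1 − 0.999^3 × 0.996^4 = 1.9% and 1 − 0.999^7 = 0.7%, giving 1.1% to 1.5% | 1.8 to 2.6 |
| Cut before the Week 12 dose | 1 − 0.996^3 = 1.2% | 1 − 0.999^3 = 0.3% | 4.0 |

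The 1.3 to 1.5 ratio applies only to the literal whole-study reading. If the X1 output stops at Week 28, as its column heading suggests, only Week 12 switchers contribute on-drug values: at most 4 of 7 panels each.

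**The case against.** The strongest reply is that Table 18 already separates the switchers. Both liver outputs also carry code X2 through Week 52, with the four placebo-to-ASP015K sequences shown apart. SAP 7.5 says the same in text, and 7.5.2.1 presents its counts by treatment group, not by randomisation arm. A reader might infer from the plot sentence that all post-switch liver values will be counted as placebo; these passages do not support that.

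A reader might also infer that a liver signal could be hidden altogether. The documents do not support that either:

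- SAP 7.5.2 gives highest AST, ALT and bilirubin categories and worst toxicity grades up to Week 12, using a maximum cut before the Week 12 dose.
- Moderate and marked abnormalities are summarised by visit, including by sequence.
- SAP 6.2 attributes adverse events after a switch to the ASP015K dose.
- Protocol Appendix 3 makes Hy's Law cases serious events.
- The DSMB reviews unblinded safety data.
- SAP 7.5.2 plans no hypothesis tests on laboratory data.

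All of this stands, and it limits the point. It does not reconcile the plot sentence with Table 18, supply a cut-off for the X1 maximum, or cover Week 12 switchers at 28/ET. Nor does X2 settle attribution fully: a single maximum per subject in a placebo-to-active sequence can come from before or after the switch, and the display does not show which.

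**Conclusion.** The concern holds in limited form. As written, the plot labels on-ASP015K peaks as placebo, the X1 highest-value table may count them as placebo, and the X1 Week 28/ET summaries can include Week 12 switchers' on-drug values under Placebo. No other output is shown to be wrong.

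The exposure shares (46% and 77%) follow from the schedule for subjects who complete 52 weeks. The arm average and the ratios in the table depend on assumed switching fractions and event rates. They show direction and rough scale, and they are not predictions. The correction is worth making before programming because it removes a discretionary choice from a key safety display.

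**What to change.** 1. **SAP 7.5.2.1 and Table 18, X1 version.** For the Placebo/100 mg/150 mg liver table and plot, use the up-to-Week-12 on-treatment maximum of Table 10, cut before the first Week 12 dose.
2. **Liver Functions Plots and whole-period table.** Replace the references to study period and randomisation arm so that both outputs follow the X2 grouping. Take switchers' maxima from their first ASP015K dose and show them under the dose received.
3. **SAP 7.11.5.** Add 28/ET to the visits at which Week 12 switchers' last pre-switch value is used, or exclude their post-switch values from the Placebo column.

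The cost is SAP wording and minor programming. No new data are needed and the pre-switch maximum is already derived. The price is that the placebo comparison of liver maxima covers 12 weeks only, which is the placebo-controlled period common to all subjects.

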### **7.5.3 Vital Signs**

Raw values and changes from baseline at each scheduled visit will be summarized using descriptive statistics.

### **7.5.4 Electrocardiograms (ECGs)**

<12-lead ECG>

- Raw values (categorical) and changes from baseline (shift from baseline) will be summarized, and the summaries will include number and percentage of subjects with normal, not clinically significant abnormal, and clinically significant abnormal 12 lead ECG findings.

<Central electrocardiogram >

QTc intervals should be calculated by followed procedure:

- Bazett's formula:  $QTc = QT/(RR/1000)^{1/2}$
- Fridericia's formula:  $QTc = QT/(RR/1000)^{1/3}$

Change for ECG variables is defined in two ways.

- baseline: before the first dose of study drug
  - predose : before the Week 4 / Week 8 dose of study drug
- 
- Descriptive statistics of the central ECG variables (QTcF, QTcB, QT, PR, RR intervals, QRS and HR) and the corresponding changes from baseline by each visit and time of measurement will be calculated. In addition, the corresponding changes from pre-dose to post-dose at Week 4 / Week 8 will be calculated.
  - The QT, QTc interval variables will be summarized by the frequencies of subjects with following categories up to Week 12, and each time points.
    - < 300 msec
    - < 330 msec
    - < 360 msec
    - > 450 msec
    - > 480 msec
    - > 500 msec
  - The change from baseline of QT, QTc interval variables will be summarized by the frequencies of subjects with following categories up to Week 12, and each time points. In addition, the corresponding changes from pre-dose to post-dose at Week 4 / Week 8 will be calculated.
    - > 30 msec increase
    - > 60 msec increase
    - > 30 msec decrease
    - > 60 msec decrease

### **7.5.5 Chest radiography**

Chest radiography will be provided as a subject listing only.

### **7.5.6 Pregnancies**

Pregnancies will be provided as a subject listing only.

## **7.6 Analysis of PK**

Refer to PK SAP.

## **7.7 Analysis of PD**

Following analysis is executed for PDAS.

Vascular Endothelial Growth Factor (VEGF), Matrix metalloproteinase 3 (MMP-3), following Lymphocytes subset variables.

- CD3+/Lymphocytes (%), CD3+ (cells/uL)
  - CD8+/Lymphocytes (%), CD8+ (cells/uL)
  - CD4+/Lymphocytes (%), CD4+ (cells/uL)
  - CD19+/Lymphocytes (%), CD19+ (cells/uL)
  - CD4/CD8 Ratio
  - (CD16 or CD56) + /Lymphocytes (%), (CD16 or CD56)+ (cells/uL)
  - (CD16+ and CD56+)/CD3- (%), CD16+ and CD56+ (cells/uL)
  - (CD16- and CD56+)/CD3- (%), CD16- and CD56+ (cells/uL)
  - (CD16+ and CD56-)/CD3- (%), CD16+ and CD56- (cells/uL)
  - (CD16- and CD56-)/CD3- (%), CD16- and CD56- (cells/uL)
  - CD56 bright/CD3- (%), CD56 bright (cells/uL)
  - CD56 dim/CD3- (%), CD56 dim (cells/uL)
- Raw values and changes from baseline will be summarized using descriptive statistics.

## **7.8 Subgroups of Interest**

Primary efficacy endpoint and selected safety variables (treatment emergent adverse events) will be summarized by the treatment group for the subgroups defined on the basis of the categorized variables listed below:

- Sex (Male, Female)
- Age Group (< 65 years, >= 65 years)
- Prior Anti-TNF DMARD Use (User, Non-user)
- Prior Biologic DMARD Use (User, Non-user)
- Duration of RA (years) (< 5 years, >= 5 years)
- Number of Prior DMARDs Used (0, 1, 2, >= 3)
- Number of Prior Biologic DMARDs Used (0, 1, 2, >= 3)
- MTX Dose (mg/week) at Baseline (0 <- 8 mg/week, 8 <- 12 mg/week, > 12 mg/week)
- Concomitant Steroid at Baseline (No, Yes)
- Prednisone Dose at Baseline (mg/day) (None, 0 <- 5 mg/day, > 5 mg/day)
- Baseline DAS28-CRP (<= 3.2, 3.2 <- 5.1, > 5.1) \*
- Baseline DAS28-ESR (<= 3.2, 3.2 <- 5.1, > 5.1) \*
- Baseline mTSS (<= Median, > Median) \*
- Baseline CRP (< 1.0, >= 1.0) \*
- Baseline Anti-CCP Antibody (Low-positive or negative (<- 3 x ULN), High-positive (> 3 x ULN)) \*
- Baseline Rheumatoid Factor (Low-positive or negative (<- 3 x ULN), High-positive (> 3 x ULN)) \*
- mTSS at Week 28 Imputation Status (Yes, No)\*\*
- Body Weight (kg) at Screening (<- 40 kg, 40 kg <- 60 kg, 60 kg <- 80 kg, > 80 kg)

\*: Only applied to efficacy analysis.

\*\* : Only applied to mTSS subgroup analysis. If mTSS at Week 28 does not exist and Week 28/ET is linear extrapolated from previous data, or switched to receive ASP015K instead of placebo at Week 12 due to the lack of efficacy, those subjects are regarded as "Yes". If mTSS at Week 28 exists and Week 28/ET is not imputed by linear extrapolation, then those subjects are regarded as "No".

For more details refer to section 7.4.1.3, 7.5.1.3.

## 7.9 Other Analyses

Not Applicable.

## 7.10 Interim Analysis (and Early Discontinuation of the Clinical Study)

Not applicable for efficacy analysis. Review of safety data and safety evaluation will be completed by an independent DSMB during the study in accordance with separate SOP.

## 7.11 Handling of Missing Data, Outliers, Visit Windows, and Other Information

### 7.11.1 Missing Data

#### PD variables

Values below the LLOQ will be set to 0 for calculation of descriptive statistics. As defined in 7.11.6, Week 12/ET, Week 28/ET, EOT are analysis visit using LOCF method.

#### Missing Data in ACR20/50/70, DAS28

Table 4 addresses the handling of missing ACR components and ACR response in the inferential analyses of ACR20/50/70, DAS28, and DAS28-related variables at Week12/ET. Note that if subject does not have any post-baseline values, then that subject will be defined as an ACR20-CRP non-responder. Moreover, if subject does not have baseline values, then that subject will be defined as an ACR20-CRP non-responder.

For ACR20/50/70, if some of ACR components include missing, then the following handling will be done.

	TJC-68	SJC-66	Remaining 5 Components	ACR20/50/70
Pattern 1	Non-Responder	Any	Any	Non-Responder
Pattern 2	Any	Non-Responder	Any	Non-Responder
Pattern 3	Any	Any	The Number of the Response is Less than 3 Components.	Non-Responder
Pattern 4	Missing	Responder or Missing	The Number of the Response is at least 3 Components, or the Number of the Missing is at least 3 Components.	Missing
Pattern 5	Responder or Missing	Missing	The Number of the Response is at least 3 Components, or the Number of the Missing is at least 3 Components.	Missing
Pattern 6	Responder or Missing	Responder or Missing	The Number of the Missing is at least 3 Components (Baseline=0 regarded as Non-Responder).	Missing
Pattern 7	Responder	Responder	The Number of the Response is at least 3 Components.	Responder

**Table4. Imputation Methods for Missing ACR and DAS28 for Components and Response at Week 12/ET**

Imputation Method		Explanation/Instruction
For use in all ACR20/50/70 analyses at Week 12/ET including primary analysis.		
1	LOCF components	
 
● First LOCF all missing ACR component value(s) at Week 12 and then calculate ACR response as Week 12/ET.
 

For use in sensitivity analysis of ACR20-CRP at Week 12/ET		
2	LOCF components and NRI response	
 
● If all ACR component values are missing at Week 12 for any reason and therefore the ACR response is missing, the missing ACR response at Week 12/ET will be imputed using NRI (i.e., subject is a non-responder).
 
● If NOT all ACR component values are missing at Week 12 for any reason, all missing ACR component value(s) at Week 12/ET will first be imputed using LOCF and then the ACR response will be calculated.
 

3	Observed	
 
● Data as observed (i.e., data as reported in the study database) will be analyzed. Missing ACR response components will remain missing if reported in the study database as missing. Missing ACR response will remain missing.
 
 
*: ACR20 at Week 12 is used for this sensitivity analysis

	Imputation Method	Explanation/Instruction
4	Multiple Imputation, assuming Missing at Random Mechanism	
Multiple imputation (MI) will be conducted in the following procedure.
 
<Step1>Imputation Part
 
1) Multiple Imputation for Non-Monotone Missing data            If non-monotone missing pattern exists, then those non-monotone missing data will be imputed by adapting Markov Chain Monte Carlo method, using each non-missing ACR components data up to Week 12. Imputation will be conducted by each ACR components (i.e. TJC-68, SJC-66, SGAP, SGA, PGA, HAQ-DI, CRP), and treatment groups, respectively.
 
2) Multiple Imputation for Monotone Missing data            Completing the imputation for non-monotone missing data, each ACR components (i.e. TJC-68, SJC-66, SGAP, SGA, PGA, HAQ-DI, CRP) at Week 12 will be imputed, respectively, based on the regression model with treatment group (Placebo, ASP015K 100 mg, ASP015K 150 mg) as factor and all values up to Week 12 as covariate. In this method, using seed as 12345, 1000 imputed datasets for each ACR components will be created based on SAS ver. 9.4 PROC MI procedure, monotone reg statement. Then, ACR20 response at Week 12 will be calculated with imputed datasets for each ACR components based on the same method described in Section 6.1.1.
 
<Step2>Analysis Part            Based on 1000 Imputed datasets created at Step1, ACR20 at Week 12 in each treatment group will be summarized by Imputed datasets. Also, the difference in ACR20 at Week 12 between ASP015K 100 mg / 150 mg and placebo and their standard error will be calculated. Moreover, the log odds ratio to placebo in ACR20 at Week 12 and its standard error will be calculated by each Imputed datasets using logistic regression model with treatment group as factor.
 
<Step3>Combine Part            In accordance with Rubin's rule (Little and Rubin, 2002), the 1000 estimated ACR20 response rate in each treatment groups are combined. In addition, the difference between ASP015K 100 mg and placebo, the difference between ASP015K 150 mg and 95% confidence interval for the difference will be combined. Moreover, the Wald's chi-squared test using logistic regression model with treatment group (Placebo, ASP015K 100 mg, ASP015K 150 mg) as factor will also be calculated.

Imputation Method	Explanation/Instruction
5	
Placebo Multiple Imputation (pMI)
 
Placebo Multiple Imputation, assuming the statistical behavior of ASP015K 100 mg or 150 mg treated patients who discontinue becomes that of placebo-treated patients after the time of dropout will be conducted in the following procedure.
 
<Step1>Imputation Part
 
1) Multiple Imputation for Non-Monotone Missing data          If non-monotone missing pattern exists, then those non-monotone missing data will be imputed by adapting Markov Chain Monte Carlo method, using each non-missing ACR components data up to Week 12. Imputation will be conducted by each ACR components (i.e. TJC-68, SJC-66, SGAP, SGA, PGA, HAQ-DI, CRP), and treatment groups, respectively.
 
2) Multiple Imputation for Monotone Missing data          Completing the imputation for non-monotone missing data, each ACR components (i.e. TJC-68, SJC-66, SGAP, SGA, PGA, HAQ-DI, CRP) at Week 12 will be imputed, respectively, based on the regression model using only data from the placebo group up to Week 12. In this method, using seed as 12345, 1000 imputed datasets for each ACR components will be created based on SAS ver. 9.4 PROC MI procedure, monotone reg statement.          Then, ACR20 response at Week 12 will be calculated with imputed datasets for each ACR components based on the same method described in Section 6.1.1.
 
<Step2>Analysis Part          For 1000 Imputed datasets created at Step1, ACR20 at Week 12 in each treatment group will be calculated. Also, the difference in ACR20 at Week 12 between ASP015K 100 mg / 150 mg and placebo and their standard error will be calculated. Moreover, the log odds ratio to placebo in ACR20 at Week 12 and its standard error will be calculated by each Imputed datasets using logistic regression model with treatment group as factor.
 
<Step3>Combine Part          In accordance with Rubin's rule (Little and Rubin, 2002), the 1000 estimated ACR20 response rate in each treatment groups are combined. In addition, the difference between ASP015K 100 mg and placebo, the difference between ASP015K 150 mg and 95% confidence interval for the difference will be combined. Moreover, the Wald's chi-squared test using logistic regression model with treatment group (Placebo, ASP015K 100 mg, ASP015K 150 mg) as factor will also be calculated.

Imputation Method		Explanation/Instruction
For use in all DAS28 and DAS28-based analyses, unless otherwise specified in Section 10.2		
Appendix 1		
6	LOCF DAS28 ACR components	
 
• LOCF all missing DAS28 ACR component value(s) and then calculate the DAS28 score.
 

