#### **Responder :**

A subject will be defined as an ACR20-CRP responder at any time point (e.g. Week 12/ET) if the subject meet ALL the following American College of Rheumatology (ACR) response criteria:

- At least 20% reduction from baseline at the time point (e.g. Week 12/ET) in the number of 68 tender joint count (TJC-68)

AND

- At least 20% reduction from baseline at the time point (e.g. Week 12/ET) in the number of 66 swollen joint count (SJC-66)

AND

- At least 20% reduction from baseline at the time point (e.g. Week 12/ET) in ANY 3 or more of the 5 following ACR components
  - Subject's global assessment of arthritis pain (SGAP) (assessed using a 100 mm VAS ; score of 0 indicates no pain, and score of 100 indicates very severe pain)
  - Subject's global assessment of arthritis (SGA) (assessed using a 100 mm VAS; score of 0 indicates no disease activity, and score of 100 mm indicates very severe disease activity)
  - Physician's global assessment of arthritis (PGA) ((assessed using a 100 mm VAS; score of 0 indicates no disease activity, and score of 100 mm indicates very severe disease activity)
  - Health Assessment Questionnaire – Disease Index (HAQ-DI; score ranges from 0 to 3 with higher scores indicating greater disability)
  - CRP (Higher values indicate greater inflammation)

Baseline is defined in Section 7.11.3. A negative percent change indicates a reduction from baseline (i.e., a favorable outcome).

If the baseline value is 0 in some of ACR components, then that component is regarded as non-responder at that component and used for ACR calculation. The handling of missing data in ACR components is described at Section 7.11.1.

Non-responder: A subject will be defined as an ACR20-CRP non-responder at the time point (e.g. Week 12/ET), if the subject does not meet the ACR20-CRP responder criteria.

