##### ACR20-CRP response at Week 12/ET

In order to assess the robustness of findings from the primary efficacy analysis, the following sensitivity analyses will be performed:

- LOCF for components and NRI for response (see Section 7.11.1. for details)

- Analysis using the PPS-ACR as the analysis set with closed testing procedure  
Note: The FAS will be replaced with the PPS as analysis set, to assess robustness results from FAS.
- Observed data (data as collected, no imputation)
- Multiple Imputation, assuming Missing at Random Mechanism (see Section 7.11.1. for details)
- Placebo Multiple Imputation (pMI) (see Section 7.11.1. for details)

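### The two ACR20 multiple-imputation sensitivity analyses impute the seven components in separate models, so same-visit residual correlation is lost; joint imputation is a cheap improvement

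*SAP*

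**What the plan says.** SAP 6.1.1 defines an ACR20 responder by improvement of at least 20% in TJC-68, in SJC-66, and "in ANY 3 or more of the 5 following ACR components".

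SAP 7.11.1, Table 4, sets out two multiple-imputation methods for Week 12: method 4 (missing at random) and method 5 (placebo multiple imputation, pMI). Both have two imputation steps.

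- **Non-monotone gaps, by MCMC:** "Imputation will be conducted by each ACR components", for all seven components and separately by treatment group.
- **Monotone missingness, by regression:** again component by component. Method 4 takes treatment group "as factor and all values up to Week 12 as covariate". Method 5 is "based on the regression model using only data from the placebo group up to Week 12". In both, "using seed as 12345, 1000 imputed datasets for each ACR components will be created".

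After that, "ACR20 response at Week 12 will be calculated with imputed datasets for each ACR components". Neither method specifies a covariance between components. The SAP does not say whether the covariates include values of the other components, or whether the seed restarts for each component.

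SAP 7.4.1.2 gives the role of these analyses: "In order to assess the robustness of findings from the primary efficacy analysis, the following sensitivity analyses will be performed". The primary ACR20 analysis (SAP 7.4.1.1) uses LOCF and Fisher's exact test.

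**The concern.** ACR20 is a joint event. Its probability depends on each component's chance of improving and also on how strongly the components improve together. A patient who drops out normally lacks all seven Week 12 values at once. If those values are drawn from seven unconnected models, nothing ties the seven residuals together, and the imputed patient qualifies as a responder too rarely. Using the other components' earlier values as covariates would preserve more of the correlation. It would not restore the part that arises at Week 12 itself.

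Of the five ACR20 sensitivity analyses, these are the only two that model the missing values and carry imputation uncertainty, and pMI is the only one that departs from missing at random by borrowing placebo behaviour. The imputed response rates in both would depend partly on a programming detail that the SAP leaves open.

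**Working it through.** The plan states no figure for these two analyses, so there is none to reproduce. The size has to come from simulation.

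**Inputs from the documents.** The ACR20 rule is in SAP 6.1.1. SAP section 4 gives design rates of 25%, 54.5% and 65.5%, 170 patients per arm, and about 10% dropout.

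**Assumptions not in the documents.** These are the correlation ρ between components, the share R² of Week 12 variance explained by earlier visits, and the probability p that a component improves (0.4 or 0.6).

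**Step 1: what separate draws do to the correlation.** Write each standardised Week 12 value as √R²·H + √(1−R²)·E, where H is the history part and E the residual, each correlated ρ across components. The correlation between two components is then:

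- joint imputation: ρ
- separate models, independent draws: R²·ρ
- separate models, identical draws: R²·ρ + (1−R²)

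With ρ = 0.6 and R² = 0.5 these are 0.60, 0.30 and 0.80.

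**Step 2: effect among imputed patients** (400,000 draws per setting). With ρ = 0.6, R² = 0.5 and p = 0.6, ACR20 is 0.411 with joint imputation, 0.331 with independent draws (8.0 points too low) and 0.469 with identical draws (5.8 points too high). Over ρ 0.4 to 0.6, R² 0.3 to 0.7 and both values of p, independent draws are 3.1 to 10.9 points too low and identical draws 3.4 to 11.9 points too high.

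**Step 3: effect on an arm.** At 10% missing, the independent-draw error is 0.10 × 3.1 to 0.10 × 10.9, or about 0.3 to 1.1 points.

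**Step 4: effect on the difference from placebo.** If a share m of each arm is imputed, the error is m·b(active) − m·b(placebo), where b is the error among imputed patients. At ρ = 0.4 and R² = 0.3, b is −7.2 points for p = 0.4 and −7.4 for p = 0.6. At 10% missing in both arms the error is 0.10 × (−7.4 + 7.2) = −0.02 points, so it nearly cancels.

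A longitudinal simulation with Weeks 4, 8 and 12 allows for less tidy cancellation. It used 200,000 patients per arm, arms calibrated to the design rates, component correlation 0.3 to 0.7 in the stable part and 0.2 to 0.6 in the visit residual, a stable variance share of 0.5 to 0.7, and dropout completely at random or dependent on the previous visit. Errors in the difference, covering both independent and identical streams, were:

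| Dropout placebo / active | Method 4, points | Method 5 against joint pMI, points |
|---|---|---|
| 10% / 10% | −0.74 to +0.59 | −0.32 to +0.14 |
| 20% / 20% | −1.53 to +1.22 | not tabulated |
| 20% / 10% | −2.37 to +1.81 | −1.85 to +1.22 |

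In method 4 at 10% dropout, single-arm rates were understated by 0.02 to 1.26 points (independent streams) or overstated by 0.40 to 1.61 points (identical stream). Joint imputation recovered the true arm rates to within about 0.15 points.

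**Step 5: scale.** At 170 per arm the standard error for 100 mg against placebo is √(0.25 × 0.75/170 + 0.545 × 0.455/170) = 0.051. For 150 mg it is √(0.25 × 0.75/170 + 0.655 × 0.345/170) = 0.049. So 0.74 points is about 0.15 of a standard error and 2.37 points about half of one. The design differences are 54.5 − 25 = 29.5 and 65.5 − 25 = 40.5 points.

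**The case against.** The strongest reply is that little hangs on this. The confirmatory test does not use multiple imputation, three other ACR20 sensitivity analyses stand beside these two, and no shift above would overturn a design-size effect. All of that stands.

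Three stronger readings are tempting, and the documents do not support them.

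- **That the correlations deciding ACR20 are lost.** Each component is regressed on earlier values, so correlation carried by patient history survives. If the unspecified covariates include the other components, more survives. Only the same-visit residual part is missing.
- **That the fixed seed is a fault.** A stated seed is ordinary practice for reproducibility. It would over-correlate the draws only if each component's run restarted the same stream and consumed it in the same way. The SAP does not say so, and no seed is given for the MCMC step.
- **That both analyses are biased in a known direction.** Independent and identical streams err in opposite directions, and the text does not settle which applies.

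It could also be said that the clearest component-by-component wording belongs to the MCMC step, whereas dropouts' Week 12 values come from the regression step. That step, however, also works on the components respectively and creates datasets for each one, so the point holds there too.

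Unequal dropout is not fanciful. In study RAJ1, adverse events led to discontinuation in 17.9% of placebo, 10.9% of 100 mg and 6.9% of 150 mg subjects (protocol 1.3). RAJ1 was single-agent therapy (protocol 2.2.2), so this is only indicative.

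**Conclusion.** The point holds as a modest specification weakness. As written, methods 4 and 5 leave same-visit residual correlation between components unmodelled, which distorts the imputed ACR20 rates. With independent draws they are about 3 to 11 points too low among imputed patients; with an identical stream, if that occurred, too high by a similar amount. The treatment difference moves by less than 1 point at the planned dropout level if dropout is equal across arms, and by about 2.4 points at most in the 20%/10% case. These sizes rest on assumed correlations, variance shares and dropout patterns. The primary ACR20 result is not affected, and a reader should not infer that the robustness conclusion would reverse at design-size effects.

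**What to change.** In methods 4 and 5, impute the seven components jointly in one PROC MI model across visits up to Week 12. Run the monotone step visit by visit, with the other components as covariates, including those already imputed at the same visit. Keep treatment as a factor for method 4 and placebo-only data for method 5; by-arm regressions are not needed to cure this problem. Use one seed for the single run, and derive ACR20 from the completed datasets.

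The cost is a change of SAP wording and a larger model. Seven components at baseline and Weeks 4, 8 and 12 make 28 variables (7 × 4), so the model may need a ridge prior to converge. If separate models are kept, the SAP should at least state which covariates enter each one and how the seed is used in each run. That would remove the ambiguity but not the missing residual correlation.
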